4.5.5 Guidelines for Elotuzumab Infusion in Subjects with Infusion Reactions

4.5.5.1 Grade 1 Infusion Reaction

Grade 1 elotuzumab infusion-related reactions by definition do not require intervention; however, increased monitoring is recommended.

4.5.5.2 Grade 2 or 3 Infusion Reaction

Infusion reactions during the elotuzumab infusion: For a Grade 2 or 3 elotuzumab infusion-related reaction, the infusion must be interrupted. The subject should be treated as clinically indicated with one or more of the following medications or interventions: antiemetics, antihistamines, analgesics, corticosteroids, leukotriene inhibitors, oxygen inhalation, epinephrine, bronchodilators, or other supportive measures as indicated.

Once the elotuzumab infusion-related reaction has resolved to Grade ≤ 1 , the infusion can be restarted at 0.5 mL/minute. If symptoms do not recur after 30 minutes, the infusion rate may be increased in a stepwise fashion (0.5 mL/minute every 30 minutes) to the rate at which the infusion reaction occurred. If no recurrence of the infusion reaction, the escalation regimen can be resumed. Subjects who experience an infusion reaction require vital signs to be monitored every 30 minutes for 1 or 2 hours after the end of the elotuzumab infusion (as clinically indicated). If the elotuzumab infusion reaction recurs, the infusion must be stopped and not restarted on that day. Appropriate therapy should be administered to address the subject's signs and symptoms. The infusion can be reattempted at the next protocol defined infusion time point at the investigator's discretion with additional premedication as described throughout Section 4.5.3.1

Infusion reactions after the completion of elotuzumab infusion: Should a Grade 2 or 3 infusion reaction occur following completion of an elotuzumab infusion, the subject should be treated as clinically indicated with 1 or more of the following medications or interventions: diphenhydramine, acetaminophen, hydrocortisone, H2 inhibitor, leukotriene inhibitor, oxygen inhalation, epinephrine, bronchodilators, or other supportive measures as indicated.

Elotuzumab infusions on subsequent weeks after a prior Grade 2 or 3 infusion reaction: Subjects with prior Grade 2 or 3 infusion reactions should have the next infusion started at 0.5 mL/min and then escalated in a stepwise fashion (0.5 mL/minute every 30 minutes) to the rate at which the infusion reaction occurred. If no Grade ≥ 2 infusion reaction occurs, the escalation regimen may be resumed and the next infusion may be initiated as planned per the regimen.

4.5.5.3 Grade 4 Infusion Reaction

Subjects with a Grade 4 elotuzumab infusion reaction must have elotuzumab permanently discontinued.

4.5.6 Treatment of Nivolumab-Related Infusion Reactions

Since nivolumab contains only human immunoglobulin protein sequences, it is unlikely to be immunogenic and induce infusion or hypersensitivity reactions. However, if such a reaction were to occur, it might manifest with fever, chills, rigors, headache, rash, pruritus, arthralgia, hypotension, hypertension, bronchospasm, or other allergic-like reactions. All Grade 3 or 4 infusion reactions should be reported within 24 hours to the study medical monitor and reported as an SAE if it meets the criteria. Infusion reactions should be graded according to NCI CTCAE (Version 3.0) guidelines.

Treatment recommendations are provided below and may be modified based on local treatment standards and guidelines, as appropriate:

For **Grade 1** symptoms: (mild reaction; infusion interruption not indicated; intervention not indicated):

• Remain at bedside and monitor subject until recovery from symptoms. The following prophylactic premedications are recommended for future infusions: diphenhydramine 50 mg (or equivalent) and/or acetaminophen/paracetamol 325 to 1000 mg at least 30 minutes before additional nivolumab administrations.

For **Grade 2** symptoms: (moderate reaction required therapy or infusion interruption but responds promptly to symptomatic treatment (eg, antihistamines, non-steroidal anti-inflammatory drugs, narcotics, corticosteroids, bronchodilators, IV fluids); prophylactic medications indicated for \leq 24 hours):

- Stop the nivolumab infusion, begin an IV infusion of normal saline, and treat the subject with diphenhydramine 50 mg IV (or equivalent) and/or acetaminophen/paracetamol 325 to 1000 mg; remain at bedside and monitor subject until resolution of symptoms. Corticosteroid and/or bronchodilator therapy may also be administered as appropriate. If the infusion is interrupted, then restart the infusion at 50% of the original infusion rate when symptoms resolve; if no further complications ensue after 30 minutes, the rate may be increased to 100% of the original infusion rate. Monitor subject closely. If symptoms recur, then no further nivolumab will be administered at that visit.
- For future infusions, the following prophylactic premedications are recommended: diphenhydramine 50 mg (or equivalent) and/or acetaminophen/paracetamol 325 to 1000 mg should be administered at least 30 minutes before nivolumab infusions. If necessary, corticosteroids (up to 25 mg of SoluCortef or equivalent) may be used.

For **Grade 3 or 4** symptoms: (severe reaction, Grade 3: prolonged [ie, not rapidly responsive to symptomatic medication and/or brief interruption of infusion]; recurrence of symptoms following initial improvement; hospitalization indicated for other clinical sequelae (eg, renal impairment, pulmonary infiltrates). Grade 4: Life-threatening; pressor or ventilator support indicated):

• Immediately discontinue infusion of nivolumab. Begin an IV infusion of normal saline and treat the subject as follows: Recommend bronchodilators, epinephrine 0.2 to 1 mg of a 1:1000 solution for subcutaneous administration or 0.1 to 0.25 mg of a 1:10,000 solution injected slowly for IV administration, and/or diphenhydramine 50 mg IV with methylprednisolone 100 mg IV (or equivalent), as needed. Subject should be monitored until the Investigator is comfortable that the symptoms will not recur. Nivolumab will be permanently discontinued. Investigators should follow their institutional guidelines for the treatment of anaphylaxis. Remain at bedside and monitor subject until recovery of the symptoms.

In case of late-occurring hypersensitivity symptoms (eg, appearance of a localized or generalized pruritus within 1 week after treatment), symptomatic treatment may be given (eg, oral antihistamine or corticosteroids).

4.5.7 Management Algorithms for Immune Related Adverse Events

Immuno-oncology (I-O) agents are associated with AEs that can differ in severity and duration than AEs caused by other therapeutic classes. Nivolumab is considered an immuno-oncology agent in this protocol. Early recognition and management of AEs associated with immuno-oncology agents may mitigate severe toxicity. Management Algorithms have been developed to assist investigators in assessing and managing the following groups of AEs:

- Gastrointestinal
- Renal
- Pulmonary
- Hepatic
- Endocrinopathy
- Skin
- Neurological

The above algorithms are found in Appendix 7 and in the nivolumab Investigator Brochure.

4.5.8 Dose Delay, Interruption, or Discontinuation for All Subjects

Please refer to Sections 4.5.8.1, 4.5.8.2, 4.5.8.3, and 4.5.8.4 for drug-specific delay guidance.

For each cohort, if the dose of one drug in the regimen (ie, pomalidomide, dexamethasone, nivolumab, or elotuzumab) is delayed, interrupted, or discontinued, the treatment with the other drugs may continue as scheduled. However, in the EPd cohort, if dexamethasone is delayed or discontinued discuss ongoing elotuzumab administration with the Medical Monitor. Subjects experiencing a 56 day delay in all study drugs due to an adverse event(s) related to study treatment must be discontinued from study drug. Subjects experiencing delays unrelated to study therapy, for example due to radiation therapy, may delay study treatment after discussion with the medical monitor.

Each cycle is 28 days. While dose delays or interruptions are permitted, the start of each cycle cannot be delayed and is fixed (ie, anchored) relative to Cycle 1 Day 1. Adjustments to the Cycle 1 Day 1 anchored schedule should not be performed. Missed doses should be skipped, not delayed, if not given within the allowed window.

Subjects may continue on study therapy even if components of the study therapy must be discontinued. For example, a subject may continue on study therapy if elotuzumab must be discontinued for an adverse event or other reason. Patients are considered still on study therapy even if they continue solely on pomalidomide, dexamethasone, or nivolumab.

4.5.8.1 Dose Delay for Elotuzumab

In Cycles 1 to 2, elotuzumab doses that fall outside of the pre-specified window of -1 to +3 days must be skipped.

Beginning with Cycle 3 and beyond, elotuzumab dosing may be delayed for up to 1 week. If unable to administer within 1 week, then the dose should be skipped and resumption of the elotuzumab continues per the protocol defined schedule.

Subjects experiencing a Grade 4 infusion reaction related to elotuzumab must permanently discontinue elotuzumab.

4.5.8.2 Dose Delay for Dexamethasone

Dexamethasone interruption should be performed as clinically indicated at the discretion of the investigator.

The weekly dexamethasone that coincides with or is temporally closest to the next elotuzumab dosing must be administered as part of the premedication for elotuzumab per the guidance in Section 4.5.3.1.

4.5.8.3 Dose Delay for Pomalidomide

Pomalidomide interruption should be performed as clinically indicated at the discretion of the investigator.

Subjects should be instructed that if a dose of pomalidomide has been missed and it has been less than 12 hours since the subject's regular dosing time, to take pomalidomide as soon as the subject remembers. If it has been more than 12 hours, the dose must be skipped. Subjects should not take 2 doses at the same time

4.5.8.4 Dose Delay for Nivolumab

Nivolumab administration should be delayed for the following:

- Any Grade ≥ 2 non-skin, drug-related adverse event, with the following exceptions:
 - Grade 2 drug-related fatigue or laboratory abnormalities do not require a treatment delay/ interruption.
- Any Grade 3 skin, drug-related adverse event
- Any Grade 3 drug-related laboratory abnormality, with the following exceptions for lymphopenia, AST, ALT, or total bilirubin or asymptomatic amylase or lipase:
 - Grade 3 lymphopenia does not require dose delay/interruption
 - If a subject has a baseline AST, ALT, or total bilirubin that is within normal limits, delay/interrupt dosing for drug-related Grade ≥ 2 toxicity.
 - If a subject has baseline AST, ALT, or total bilirubin within the Grade 1 toxicity range, delay/interrupt dosing for drug-related Grade \geq 3 toxicity.
 - Any Grade \geq 3 drug-related amylase or lipase abnormality that is not associated with symptoms or clinical manifestations of pancreatitis does not require dose delay/interruption.
- Any adverse event, laboratory abnormality, or intercurrent illness which, in the judgment of the investigator, warrants delaying the dose of study medication.

Revised Protocol No.: 03 Date: 08-Mar-2018 Subjects who require delay/interruption of nivolumab should be re-evaluated as clinically indicated and resume nivolumab dosing, as per the protocol dosing schedule when re-treatment criteria are met.

4.5.8.5 Criteria to Resume Treatment with Nivolumab

Subjects may resume treatment with nivolumab when the drug-related AE(s) resolve(s) to Grade ≤ 1 or baseline, with the following exceptions:

- Subjects may resume treatment in the presence of Grade 2 fatigue
- Subjects who have not experienced a Grade 3 drug-related skin AE may resume treatment in the presence of Grade 2 skin toxicity
 - Subjects with baseline Grade 1 AST/ALT or total bilirubin who require dose delays/interruptions for reasons other than a 2-grade shift in AST/ALT or total bilirubin may resume treatment in the presence of Grade 2 AST/ALT OR total bilirubin
 - Subjects with combined Grade 2 AST/ALT AND total bilirubin values meeting discontinuation parameters (Section 4.5.8.6) should have treatment permanently discontinued
- Drug-related pulmonary toxicity, diarrhea, colitis, uveitis or neurologic toxicity must have resolved to baseline before treatment is resumed. Subjects with persistent Grade 1 pneumonitis after completion of a steroid taper over at least 1 month may be eligible for retreatment if discussed with and approved by the BMS Medical Monitor.
- Drug-related endocrinopathies adequately controlled with only physiologic hormone replacement may resume treatment after consultation with the BMS Medical Monitor

Dose delay/interruption of nivolumab which results in treatment interruption of > 8 weeks require treatment discontinuation, with exceptions as noted in Section 4.5.8.6. There will be no dose reductions for nivolumab.

4.5.8.6 Nivolumab Dose Discontinuation

Nivolumab treatment should be permanently discontinued for the following:

- Any Grade 2 drug-related uveitis, eye pain or blurred vision that does not respond to topical therapy and does not improve to Grade 1 severity within the re-treatment period OR requires systemic treatment
- Any Grade 3 non-skin, drug-related adverse event lasting > 7 days, with the following exceptions for laboratory abnormalities, drug-related uveitis, pneumonitis, bronchospasm, hypersensitivity reactions, infusion reactions, and endocrinopathies:
 - Grade 3 drug-related uveitis, pneumonitis, bronchospasm, hypersensitivity reaction, or infusion reaction of any duration requires discontinuation
 - Grade 3 drug-related endocrinopathies adequately controlled with only physiologic hormone replacement do not require discontinuation
 - Grade 3 drug-related laboratory abnormalities do not require treatment discontinuation except:
 - Grade 3 drug-related thrombocytopenia > 7 days or associated with bleeding requires

discontinuation

- Any drug-related liver function test (LFT) abnormality that meets the following criteria require discontinuation:
 - AST or ALT > 5-10 x ULN for 2 weeks
 - AST or $ALT > 10 \times ULN$
 - Total bilirubin > 5 x ULN
 - Concurrent AST or $ALT > 3 \times ULN$ and total bilirubin $> 2 \times ULN$
 - Any Grade 4 drug-related adverse event or laboratory abnormality, except for the following events which do not require discontinuation:
- Grade 4 neutropenia \leq 7 days
- Grade 4 lymphopenia or leukopenia
- Isolated Grade 4 amylase or lipase abnormalities that are not associated with symptoms or clinical manifestations of pancreatitis. The BMS Medical Monitor should be consulted for Grade 4 amylase or lipase abnormalities.
- Isolated Grade 4 electrolyte imbalances/abnormalities that are not associated with clinical sequelae and are corrected with supplementation/appropriate management within 72 hours of their onset
- Grade 4 drug-related endocrinopathy adverse events, such as adrenal insufficiency, ACTH deficiency, hyper- or hypothyroidism, or glucose intolerance, which resolve or are adequately controlled with physiologic hormone replacement (corticosteroids, thyroid hormones) or glucose-controlling agents, respectively, may not require discontinuation after discussion with and approval from the BMS Medical Monitor.
- Any event that leads to delay in dosing lasting > 8 weeks from the previous dose requires discontinuation, with the following exceptions:
 - Dosing delays to allow for prolonged steroid tapers to manage drug-related adverse events are allowed. Prior to re-initiating treatment in a subject with a dosing delay lasting > 8 weeks from the previous dose, the BMS medical monitor must be consulted. Tumor assessments should continue as per protocol even if dosing is delayed/interrupted. Periodic study visits to assess safety and laboratory studies should also continue as clinically indicated during such dosing delays/interruption.
 - Dosing delays lasting > 8 weeks from the previous dose that occur for non-drug-related reasons may be allowed if approved by the BMS medical monitor. Prior to re-initiating treatment in a subject with a dosing delay lasting > 8 weeks, the BMS medical monitor must be consulted. Tumor assessments should continue as per protocol even if dosing is delayed/interrupted. Periodic study visits to assess safety and laboratory studies should also continue as clinically indicated during such dosing delays/interruption.
- Any adverse event, laboratory abnormality, or intercurrent illness which, in the judgment of the Investigator, presents a substantial clinical risk to the subject with continued nivolumab dosing.

4.5.9 Recommended Dose Reduction

The criteria presented in this section for dose modification of dexamethasone and pomalidomide are meant as general guidelines. They are based on current US standards of clinical practice. Dose
modification may occur in the setting of lower grade toxicity if the investigator, in consultation with the Medical Monitor/Sponsor, believes that it is in the interest of subject safety.

4.5.9.1 Elotuzumab and Nivolumab

No dose reduction is allowed for elotuzumab or nivolumab.

4.5.9.2 Dexamethasone

Dexamethasone dose reductions for toxicity related to study drug, must be performed as clinically indicated. Recommended management is described in Table 4.5.9.2-1 and Table 4.5.9.2-2. Deviations to the recommended dose reductions are allowed based on the clinical judgment of the investigator.

CTCAE Category	Adverse Event	Treatment Adjustment					
Gastrointestinal	Dyspepsia, gastric or duodenal ulcer, gastritis	Treat with a proton pump inhibitor.					
	Grade 1 - 2 (requiring medical management)	If symptoms persist despite above measures, decrease by 1 dose level.					
	≥ Grade 3 (requiring hospitalization or surgery)	Hold dexamethasone until symptoms are adequately controlled. Reduce by 1 dose level and resume along with concurrent therapy with a proton pump inhibitor.If symptoms persist despite above measures, reduce to dose level -3 (dose withheld).					
	Acute pancreatitis	Reduce to dose level -3 (dose withheld).					
Cardiovascular	Edema ≥ Grade 3 (limiting function and unresponsive to therapy or anasarca)	Use diuretics as needed, and decrease dexamethasone by 1 dose level. If edema persists despite above measures, decrease by another dose level.					
Neurology	Confusion or Mood alteration	Hold dexamethasone until symptoms resolve.					
	\geq Grade 2 (interfering with	Decrease by 1 dose level and resume.					
	activities of daily living)	If symptoms persist despite above measures, decrease by another dose level.					
Musculoskeletal	Muscle weakness ≥ Grade 2 (symptomatic and interfering with function ± interfering with activities of daily living)	Hold dose until muscle weakness is ≤ Grade 1. Decrease dexamethasone by 1 dose level and resume. If weakness persists despite above measures, decrease by another dose level.					
Metabolic	Hyperglycemia \geq Grade 3 or higher	Treat with insulin or oral hypoglycemics as needed. If uncontrolled despite above measures, decrease by 1 dose level until glucose levels are satisfactory.					
Constitutional	Insomnia \geq Grade 2	Decrease by 1 dose level and resume.					

Table 4.5.9.2-1:Dexamethasone Dose Reductions

Dose reduction for persistent Grade 2 or Grade \geq 3 AEs believed to be related to dexamethasone and not listed above are permitted.

Revised Protocol No.: 03 Date: 08-Mar-2018 Contact the medical monitor to discuss dexamethasone premedication for subjects who reach dose level -3 or must discontinue dexamethasone due to toxicity.

Dose Level	Reducing Dexameth Weeks with Elotuz	asone on zumab	Reducing Dexamethasone on Weeks Without Elotuzumab			
	РО	IV	РО	IV		
0	\leq 75 years old - 28 mg	8 mg	\leq 75 years old - 40 mg	N/A		
	> 75 years old - 8 mg		> 75 years old - 20 mg			
-1	\leq 75 years old - 12 mg	8 mg	\leq 75 years old - 20 mg	N/A		
	> 75 years old - 8 mg		> 75 years old - 12 mg			
-2	\leq 75 years old - 0 mg	8 mg	\leq 75 years old - 12 mg	N/A		
	> 75 years old - 0 mg		> 75 years old - 8 mg			
-3	\leq 75 years old - 0 mg	Contact	\leq 75 years old - 0 mg	N/A		
	> 75 years old - 0 mg	Monitor	> 75 years old - 0 mg			

Table 4.5.9.2-2:Dexamethasone Dose Levels

4.5.9.3 Pomalidomide

Below are the recommended dose adjustments for the management of NCI CTCAE Grade 3 and 4 toxicities for thrombocytopenia and neutropenia judged by the investigator to be related to pomalidomide. Information in Table 4.5.9.3-1 and Table 4.5.9.3-2 is based on pomalidomide prescribing information, which contains additional guidance on pomalidomide dosing.^{29,31}

Table 4.5.9.3-1:	Treating Thrombocytopenia Related to Pomalidomide
------------------	---

When Platelet Count:	Recommended Course:
Fall to $< 25,000 \text{ per mm}^3$	Interrupt pomalidomide treatment, follow Complete Blood Count weekly.
Return to $> 50,000$ per mm ³	Resume pomalidomide at 3 mg daily
For each subsequent drop $< 25,000 \text{ mm}^3$	Interrupt pomalidomide treatment
Return to \geq 50,000 mm ³	Resume pomalidomide at 1 mg less than previous dose

Table 4.5.9.3-2: Treating Neutropenia Related to Pomalidomide

When Neutrophil Count:	Recommended Course:
Fall to < 500 per mm ³ or febrile neutropenia (fever $\ge 38.5^{\circ}$ C and ANC $< 1,000 \text{ mm}^3$)	Interrupt pomalidomide treatment, follow Complete Blood Count weekly.
ANC returns to $\geq 500 \text{ per mm}^3$	Resume pomalidomide at 3 mg daily

When Neutrophil Count:	Recommended Course:
For each subsequent drop $< 500 \text{ mm}^3$	Interrupt pomalidomide treatment
Return to $\geq 500 \text{ mm}^3$	Resume pomalidomide at 1 mg less than previous dose

ANC, absolute neutrophil count.

If necessary to co-administer strong inhibitors of CYP1A2 in the presence of strong inhibitors of CYP3A4 and P-glycoprotein, consider reducing pomalidomide dose by 50%.^{29,31}

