7.4.1.7 Infusion Interruption

The number and percentage of subjects with any interruption in their elotuzumab infusion, with 1, 2, 3, or ≥ 4 interruptions, with an interruption due to "infusion reaction", "infusion administration issues" and "other" will be presented. In addition, duration of interruptions (in minutes) will be summarized via descriptive statistics.

A subject listing will be generated for elotuzumab IV interruptions. This listing will include reason for interruption, whether the interruption was resumed, and duration of the interruption.

The number and percentage of subjects with any elotuzumab IV rate reduction, with 1, 2, 3, or ≥ 4 rate reductions, and with rate reductions due to "infusion reaction," "infusion administration issues," and "other" will be presented.

A listing will be generated for elotuzumab IV rate reductions.

7.4.1.8 *Pomalidomide*

The number and percentage of subjects with a dose reduction, omission and discontinuation which will be collected on the records from the dosing CRF page.

Reduction of Pomalidomide will also be computed based on the actual dose received. In any study day (excluding, cycle 1, day 1), the drug will have a calculated reduction compared to the

previous day, if the actual level of the administered dose is below the actual level of the administered dose in the previous instance. The information for this analysis will be derived programmatically, using

the total daily dose on the "Record of Study Medication - pomalidomide" eCRF page. The daily dose levels are defined as follows:

- Dose level 0 or full dose (4mg)
- Dose level -1 (3mg)
- Dose level -2 (2mg)
- Dose level -3 (1mg)

The number and percentage of subjects with a dose reduction, and the lowest dose level achieved per subject (-1, -2, -3), will be presented.

The reason for dose reduction as reported by the investigator will be tabulated for all instances with a calculated reduction based on the dose modification for Pomalidomide page. A category "unknown" will be defined for all calculated reductions with no reason reported by the investigator.

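### The first-event row in both pomalidomide tables is a fixed 3 mg; read literally, it raises the dose of a subject already at 2 mg or 1 mg

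*Protocol*

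**What the plan says.** Section 4.5.1 of the protocol sets pomalidomide at 4 mg daily for the first three weeks of a four-week cycle. Section 4.5.9.3 gives the recommended adjustments for pomalidomide-related cytopenia in Table 4.5.9.3-1 (platelets below 25,000 per mm³) and Table 4.5.9.3-2 (neutrophils below 500 per mm³, or febrile neutropenia).

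Both tables have the same structure:

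- First event: interrupt, follow counts weekly and, on recovery, "Resume pomalidomide at 3 mg daily". This is a fixed dose.
- Each later drop in that table's own count: interrupt and, on recovery, "Resume pomalidomide at 1 mg less than previous dose". This is relative to the current dose.

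The same section has a conditional sentence on drug interactions: "If necessary to co-administer strong inhibitors of CYP1A2 in the presence of strong inhibitors of CYP3A4 and P-glycoprotein, consider reducing pomalidomide dose by 50" per cent. It also says that the prescribing information is the basis of the tables, "which contains additional guidance on pomalidomide dosing".

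Section 4.5.9 limits the force of all this. The criteria for "dose modification of dexamethasone and pomalidomide are meant as general guidelines", and dose "modification may occur in the setting of lower grade toxicity if the investigator, in consultation with the Medical Monitor/Sponsor", judges it to be in the interest of subject safety.

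The SAP foresees doses below 3 mg. In Section 7.4.1.8, levels -2 and -3 are 2 mg and 1 mg, and "the lowest dose level achieved per subject (-1, -2, -3), will be presented".

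**The concern.** A fixed 3 mg is a step down only from 4 mg. From 2 mg or 1 mg it is a step up. The supplied text of the protocol and SAP contains no sentence that caps the resumed dose at the dose held when the event occurred. (Section 3.4 is not part of the supplied text.)

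The tables count events separately. A subject can therefore be well down the dose scale for one cytopenia and still be at a first event for the other. The written recommendation, under a heading about dose reduction, would then increase the drug judged to have caused the event.

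EPd enrollment is closed (Synopsis, Study Design). The point therefore concerns EPd subjects still on treatment and EN subjects who cross over to EPd, out of about 30 planned for EN.

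**Working it through.** The plan gives no figure of its own to reproduce. The check is to apply the two tables as written and compare doses before and after.

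**Inputs**

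- Starting dose 4 mg on 21 days per cycle (Section 4.5.1).
- First event in a table: resume at 3 mg. Later event in the same table: current dose minus 1 mg (Tables 4.5.9.3-1 and 4.5.9.3-2).
- Interaction sentence: 50% of 4 mg = 2 mg (Section 4.5.9.3).

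**Dose paths read literally** (N = neutropenia, T = thrombocytopenia; exchanging N and T gives the same doses)

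| Events | Daily dose, mg | Last step |
|---|---|---|
| N | 4, 3 | down |
| N, N | 4, 3, 2 | down |
| N, T | 4, 3, 3 | unchanged |
| N, N, T | 4, 3, 2, 3 | **up** |
| N, N, N, T | 4, 3, 2, 1, 3 | **up** |
| Interaction cut, then N or T | 4, 2, 3 | **up** |

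By the tables alone, a rise from 2 mg needs two earlier events of the other cytopenia, and a rise from 1 mg needs three. Of the eight possible orders of three events, two (N, N, T and T, T, N) include a rise. These are counts of orders, not probabilities, because the documents give no event rates.

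**Size per full cycle**

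Full-cycle dose = daily dose × 21. After resumption under the first-event row it is always 3 × 21 = 63 mg.

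| Dose at event | Full cycle before | Full cycle after | Change |
|---|---|---|---|
| 4 mg | 84 mg | 63 mg | (63 − 84)/84 = −25% |
| 3 mg | 63 mg | 63 mg | 0% |
| 2 mg | 42 mg | 63 mg | (63 − 42)/42 = +50% |
| 1 mg | 21 mg | 63 mg | (63 − 21)/21 = +200% |

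The cycle containing the event is left out. Its dose is lower because treatment is interrupted while cycle starts stay fixed (Section 4.5.8), and the length of interruption is not specified.

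**Does another reading remove the problem?**

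Suppose a later drop meant a drop in either count. Then N, N, T would give 4, 3, 2, 1 mg and the cross-table rise would disappear. But each row names only its own count. Even on that reading, a subject at 2 mg because of the interaction sentence would go to 3 mg at a first event.

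**The case against.** The strongest reply is that no one would apply the row this way. The section is about reducing doses, the protocol dose is 4 mg, and the first row plainly pictures the first step down from it. The tables are recommendations. Section 4.5.8.3 leaves interruption to the investigator, Section 4.5.9 allows modification even for lower-grade toxicity after consultation, and Section 3.5 requires investigational product to be stopped when an adverse event or laboratory abnormality makes continuing contrary to the subject's interest. Section 5.2 supplies the package insert to sites, and it may already state the missing limit. The interaction sentence only asks the investigator to consider a cut and, while the inhibitors continue, can be read as still applying to the resumed dose.

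Most of this stands, and it is why the point is minor. It does not correct the row. What the prescribing information says cannot be known from the documents, and discretion to depart from a recommendation does not make the recommendation right.

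A reader might go further and infer that the 3 mg to 3 mg case is also an error: a subject reduced for one cytopenia has a first event of the other and is not reduced again. The documents do not support that. Nothing in them requires a first event of a different cytopenia to trigger a further cut. Treatment is still interrupted until counts recover, and Section 4.5.9 leaves room for a further reduction. SAP Section 7.4.1.8 would not count this as a reduction, since it counts one only "if the actual level of the administered dose is below the actual level of the administered dose in the previous instance", but that is a reporting definition and not a dosing standard. A mandatory step to 2 mg would take a full cycle from 63 to 42 mg (−33%) and might depart from the prescribing information.

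**Conclusion.** The point holds in a narrow form. Followed literally, the first-event row raises pomalidomide after a severe cytopenia in a subject already at 2 mg (+50% per full cycle) or 1 mg (+200%). This rests on two assumptions: that each table's event count is separate, as its rows are worded, and that no limit is stated in material outside the supplied text.

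The cases are rare in the sense that they need two or three events of one cytopenia before the first of the other, or an earlier reduction for another reason. How many subjects are affected is unknown, and the percentages describe individual dose paths, not an expected effect on the trial. No efficacy or sample-size figure is touched. Given the guideline status of the tables, this is a minor safety correction.

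Whether a subject at 3 mg or below should step down a further 1 mg after a first event of the other cytopenia is a clinical choice for the sponsor and Medical Monitor, not an error in the plan.

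**What to change.** First check the wording against the prescribing information. Then amend both tables in two places:

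1. Limit the 3 mg first-event row to subjects taking 4 mg when the event occurs.
2. State that pomalidomide is never resumed above the dose held at the event.

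The ordinary step from 4 to 3 mg is unchanged. If the sponsor also wants a further 1 mg step for subjects already reduced, it can be added as a deliberate decision, but the correction does not depend on it.

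The cost is one wording amendment with IRB/IEC approval (Section 9.1.1), and no extra patients, visits or tests. The downside is lower exposure than under the literal row in the few subjects concerned. With the cap alone it is at least 63 − 42 = 21 mg less per full cycle for a subject at 2 mg, and at least 63 − 21 = 42 mg less for a subject at 1 mg.
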